9.4.4 Safety Analyses

Primary endpoint: The difference in bacterial reduction between the experimental group (laser) and the comparison group (routinely used irrigation protocol) by measuring reduction in colony forming units (CFU). Friedman's and Wilcoxon signed-rank tests will be used to compare the amount of bacteria before and after treatment in both groups, with significance levels set at 5% (P < 0.05).

The resident performing the endodontic treatment will evaluate and treatment plan the case as routinely performed through a clinical and radiographic examination of the involved teeth. At least one periapical radiograph of the involved tooth will be obtained during the consultation as routine protocol requires for every root canal treatment. In order to be eligible to participate in this study, an individual must meet all of the previously mentioned criteria (check section 5.1 and 5.2). On the day of procedure, the resident will conduct and complete the root canal treatment as standard

protocol requires, including medical history review/update, clinical assessment, vital signs (blood pressure). Participants, providers and observers will wear appropriate laser protection eyewear (OD 3 or greater) whenever the laser is in use.

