8.3.4.2 Relationship to Study Intervention

All adverse events (AEs) must have their relationship to laser assessed by the clinician who examines and evaluates the participant based on temporal relationship and his/her clinical judgment. The degree of certainty about causality will be graded using the categories below. In a clinical trial, the study product must always be considered.

- Related – The AE is known to occur with the laser, there is a reasonable possibility that the laser caused the AE, or there is a temporal relationship between the laser and event. Reasonable possibility means that there is evidence to suggest a causal relationship between the laser and the AE.
- Not Related – There is not a reasonable possibility that the administration of the laser caused the event, there is no temporal relationship between the laser and event onset, or an alternate etiology has been established.

OR

- Definitely Related – There is clear evidence to suggest a causal relationship, and other possible contributing factors can be ruled out. The clinical event, including an abnormal laboratory test result, occurs in a plausible time relationship to laser administration and cannot be explained by concurrent disease or other drugs or chemicals. The response to withdrawal of the laser group (dechallenge) should be clinically plausible. The event must be pharmacologically or phenomenologically definitive, with use of a satisfactory rechallenge procedure if necessary.
- Probably Related – There is evidence to suggest a causal relationship, and the influence of other factors is unlikely. The clinical event, including an abnormal laboratory test result, occurs within a reasonable time after administration of the laser, is unlikely to be attributed to concurrent disease or other drugs or chemicals, and follows a clinically reasonable

response on withdrawal (dechallenge). Rechallenge information is not required to fulfill this definition.

- Possibly Related – There is some evidence to suggest a causal relationship (e.g., the event occurred within a reasonable time after administration of the laser). However, other factors may have contributed to the event (e.g., the participant's clinical condition, other concomitant events). Although an AE may rate only as "possibly related" soon after discovery, it can be flagged as requiring more information and later be upgraded to "probably related" or "definitely related", as appropriate.

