8.3.5 Time Period and Frequency for Event Assessment and Follow-Up

Safety will be assessed by monitoring and recording potential adverse effects using the CTCAE at each study visit. Participants will be monitored by medical histories, physical examinations. If CTCAE grading does not exist for an adverse event, the severity of mild, moderate, severe, life-threatening, and death, corresponding to Grades 1-5, will be used whenever possible.

At each contact with the subject, the investigator will seek information on adverse events by non-directive questioning and, as appropriate, by examination. Adverse events may also be detected when they are volunteered by the subject during the screening process or between visits, or through physical examination, laboratory test, or other assessments. Information on all adverse events will be recorded in the source documentation. To the extent possible, adverse events will be recorded as a diagnosis and symptoms used to make the diagnosis recorded within the diagnosis event.

As much as possible, each adverse event or follow-up information will be evaluated to determine:

1. Severity grade (CTCAE Grade 1-5)
2. Duration (start and end dates)
3. Relationship to the study treatment or process – [Reasonable possibility that AE is related: No (unrelated/ not suspected) or Yes (a suspected adverse reaction)]. If yes (suspected) - is the event possibly, probably or definitely related to the investigational treatment?
4. Expectedness to study treatment or process – [Unexpected – if the event severity and/or frequency is not described in the investigator brochure or protocol].
5. Action taken with respect to study or investigational treatment or process (none, dose adjusted, temporarily interrupted, permanently discontinued, unknown, not applicable)
6. Whether medication or therapy taken (no concomitant medication/non-drug therapy, concomitant medication/non-drug therapy)
7. Whether the event is serious

Once an adverse event is detected, it should be followed until its resolution or until it is judged to be permanent, and assessment should be made at each visit (or more frequently, if necessary) of any changes in severity, the suspected relationship to the study treatment, the interventions required to treat it, and the outcome.

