8.3.6 Adverse Event Reporting

Reporting Period

Adverse events will be reported from the time of informed consent until study completion.

Investigator Reporting: Notifying the Study Sponsor

N/A

Investigator Reporting: Local Reporting Requirements

The investigator will report AEs and SAEs to the IRB/EC of record and other local regulatory groups per the local requirements.

New information regarding the SAE will be reported as it becomes available and in the same manner that the initial SAE (i.e. SAE form). The investigator will follow the event to resolution or until the event is deemed and documented irreversible, whichever is longer.

8.3.7 *Serious Adverse Event Reporting*

The study investigator shall complete an Unanticipated Adverse Device Effect Form and submit to the reviewing Institutional Review Board (IRB) . The study investigator is responsible for conducting an evaluation of an unanticipated adverse device effect and shall report the results of such evaluation to the Food and Drug Administration (FDA) and to all reviewing IRBs and participating investigators per the applicable regulation.

8.3.8 *Reporting Events to Participants*

N/A

8.3.9 *Events of Special Interest*

N/A

8.3.10 *Reporting of Pregnancy*

Pregnancy, in and of itself, is not regarded as an AE unless there is suspicion that study device or process may have interfered with the effectiveness of a contraceptive medication or method. When a pregnancy has been confirmed in a subject, and the fetus is exposed to study device and/or process (maternally or paternally), the following procedures should be followed to ensure subject safety:

Data on fetal outcome are collected for regulatory reporting and device safety evaluation. Follow-up should be conducted for each pregnancy to determine outcome, including spontaneous or voluntary termination, details of the birth, and the presence or absence of any birth defects, congenital abnormalities, or maternal and/or newborn complications.

8.4 *Unanticipated Problems*

8.4.1 *Definition of Unanticipated Problems (UP)*

The Office for Human Research Protections (OHRP) considers unanticipated problems involving risks to participants or others to include, in general, any incident, experience, or outcome that meets all the following criteria:

- Unexpected in terms of nature, severity, or frequency given (a) the research procedures that are described in the protocol-related documents, such as the Institutional Review Board

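### Section 9.4.4, Safety Analyses, sets out the CFU efficacy tests, and nothing in section 9 analyses adverse events

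*Combined protocol and SAP*

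**What the plan says.** Section 9.4.4 has two parts. The first is the primary efficacy endpoint, "Primary endpoint: The difference in bacterial reduction between the experimental group (laser) and the comparison group (routinely used irrigation protocol", followed by its tests: "Friedman's and Wilcoxon signed-rank tests will be used to compare the amount of bacteria before and after treatment in both groups". The second is procedural and begins "The resident performing the endodontic treatment will evaluate and treatment plan the case as routinely performed". It covers the consultation radiograph, eligibility, blood pressure and laser eyewear.

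AE collection is described elsewhere. Section 8.3.5 states: "Safety will be assessed by monitoring and recording potential adverse effects using the CTCAE at each study visit". Section 8.3.6 sets the period: "Adverse events will be reported from the time of informed consent until study completion". Neither limits collection to one arm.

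Causality is worded in two ways. Section 8.3.4.2 says: "All adverse events (AEs) must have their relationship to laser assessed by the clinician who examines and evaluates the participant", and each of its categories refers to the laser. Item 3 of section 8.3.5 first asks, as a yes/no question, about "Relationship to the study treatment or process". If the answer is yes, it asks "is the event possibly, probably or definitely related to the investigational treatment".

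**The concern.** An analyst who carries out section 9.4.4 as written would run a before/after comparison of bacterial counts and file it as the safety result. It would contain no event, no participant count and no comparison of arms. The AE data would be collected for up to two years per participant with no stated use, so any summary that did appear would be chosen after the data were known, by a team that section 6.3 says cannot be blinded.

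This matters because the arms differ in more than the laser. Under section 4.1 the control arm is instrumented with 3% NaOCl and the laser arm with saline followed by laser activation. Section 2.2 gives the wish to use less harsh chemicals as part of the motive, and it also mentions heat damage to adjacent tissue as a limit on laser use in canals. Section 2.2.3 nevertheless states that the device has no known adverse effects. Event rates by arm are the natural check on these statements, and the plan does not provide for them.

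**Working it through.** **Step 1. Section 9.4.4 against its apparent sources.** The endpoint and test sentences match section 9.4.2, including the 5% significance level. The remaining text matches section 8.2. Once both are removed, nothing specific to safety analysis remains. The named tests are within-group tests of bacterial counts before and after treatment, so they could not compare the arms on harm whatever the heading.

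**Step 2. Is an AE analysis given elsewhere in section 9?**
- 9.1 and 9.2: hypotheses and sample size for CFU only.
- 9.3: describes who is recruited; no safety set and no rule on treatment received.
- 9.4.1: a generic rule for describing categorical and continuous data; names neither AEs nor arms.
- 9.4.3: pain scores and treatment success as secondary endpoints; no AEs.
- 9.4.5: baseline characteristics only.
- 9.4.6 to 9.4.9: not applicable.

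So no AE analysis is specified.

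**Step 3. Would the data exist?** Yes. Sections 8.3.5 and 8.3.6 provide for severity grade, dates, relatedness, expectedness and seriousness, from consent to completion. The gap is in the analysis, not in data collection.

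**Step 4. Could related events be compared between arms?** Under 8.3.4.2, causality is judged against the laser. Control participants receive none, so their events can hardly be graded as anything but unrelated. Under 8.3.5 item 3, the yes/no question is broader and a control event could be marked related, but the degree of certainty again refers to the investigational treatment. The two sections can classify the same control-arm event differently. A comparison of all events regardless of cause does not depend on either.

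**Step 5. What a by-arm table could show (illustration only).** The denominators come from section 9.2. For a two-sided independent t test with effect size 0.8, alpha 0.05 and power 0.80, the noncentral t calculation gives 25.5, so 26 per group and 52 in all. For 30% attrition, 26 / (1 − 0.30) = 37.1, so 38 per group and 76 in all. Both stated figures reproduce. They were set for CFU, and the documents give no figure for safety.

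With zero events among n participants, the exact two-sided 95% upper limit is 1 − 0.025^(1/n):
- n = 38: 1 − 0.025^(1/38) = 9.3%
- n = 26: 1 − 0.025^(1/26) = 13.2%

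Power of a two-sided Fisher exact test at 0.05 with 38 per arm, under assumed AE rates that are not in the documents:

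| Assumed rates | Power |
|---|---|
| 10% v 20% | 15% |
| 20% v 40% | 40% |
| 10% v 30% | 50% |
| 5% v 25% | 61% |
| 10% v 40% | 83% |

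Only very large differences would be detected reliably, so the summary should be descriptive, with intervals.

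**The case against.** The best defence is that section 9.4.4 is a copying slip in a postmarket study of an FDA-cleared device. Section 3 lists no safety objective and section 9.1 no safety hypothesis. AEs will still be recorded and reported to the IRB, and the generic rule in 9.4.1 could be stretched to cover a count of events. On this view an AE table would be produced anyway.

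That probably describes what would happen, and it tempers the consequence: nothing in the documents shows that anyone intends to rest a safety claim on a bacterial count. It does not rescue the text. The section states an analysis, and it is the wrong one. A table produced anyway would have no stated denominator, severity cut-off or basis for comparison.

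A reader might go further and infer that relatedness is graded only to the laser throughout, so that no control-arm event could ever be called related and the safety comparison is biased. The documents do not support that. Section 8.3.5 item 3 opens with a broader question, no section plans a table of related events, and laser-only grading does not affect a comparison of all events. What stands is narrower: 8.3.4.2 and 8.3.5 disagree, and grading against the laser alone cannot support a between-arm comparison of related events.

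Nor should the 9.3% and 13.2% limits be read as the size of the defect. They follow from the sample size and would be the same under a perfect section 9.4.4. They also take the arm sizes as given, which simple randomization (section 6.3) does not guarantee, and they suit rare events only: section 8.3.4.3 expects pain, swelling and discomfort, so zero events of any kind is implausible.

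**Conclusion.** Wrong as written. Section 9.4.4 prescribes an efficacy analysis under a safety heading, and no AE analysis appears anywhere in section 9, although the data for one are to be collected in all participants. This conclusion rests on the text alone and needs no assumption. It has no numerical magnitude. The limits in the working show only that even a clean result for a rare event would be compatible with a risk of about 9% to 13%, given 38 or 26 participants, which is why intervals belong in the table.

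The CFU analysis and its sample size are not affected by this point. The disagreement over relatedness is a secondary issue. It restricts how related events may be used, but it does not show that the trial's safety data are biased.

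**What to change.** Replace the whole text of section 9.4.4 with a descriptive safety summary:

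1. Denominator: treated participants, grouped by treatment received.
2. For each arm, the number and percentage with any AE, any severe AE and any serious AE, with exact 95% intervals.
3. Compare the arms on all events regardless of attributed cause.
4. Define severe by the CTCAE grades of section 8.3.5, with the cut-off stated in advance and reconciled with the mild/moderate/severe scale of section 8.3.4.1.
5. Report unanticipated adverse device effects for the laser arm only. Section 8.3.3 defines them as caused by or associated with a device, so a control column would be uninformative.
6. Show relatedness as a listing, and reconcile section 8.3.4.2 with section 8.3.5 item 3 so that both ask the same question.
7. Say whether pain reported on the surveys counts as an AE, since it is both a secondary endpoint and an expected event.

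The cost is one replaced paragraph, one small table and two wording reconciliations in section 8.3. It needs no new data, visits or participants. The change should be made before AEs are tabulated by arm.

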9.4.5 Baseline Descriptive Statistics

The baseline demographic and clinical characteristics of the study population, including age, gender, pre-op pain and endodontic diagnosis will be analyzed using descriptive statistics. Descriptive statistics will be presented as counts, proportions (%), mean and standard deviation whenever appropriate. The demographic and clinical characteristics of the study population will be analyzed using the Fisher's Exact Test. P-value of ≤ 0.05 will be considered statistically significant.

9.4.6 Planned Interim Analyses

N/A

9.4.7 Sub-Group Analyses

N/A

9.4.8 Tabulation of Individual Participant Data

N/A

9.4.9 Exploratory Analyses

N/A

10 SUPPORTING DOCUMENTATION AND OPERATIONAL CONSIDERATIONS

10.1 Regulatory, Ethical, and Study Oversight Considerations

10.1.1 Informed Consent Process

10.1.1.1 Consent/Accent and Other Informational Documents Provided To Participants

Consent forms describing in detail the laser device, study procedures, and risks are given to the participant and written documentation of informed consent is required prior to enrolling the subject in the study. The following consent materials are submitted with this protocol (*attachment 5*).

10.1.1.2 Consent Procedures and Documentation

Informed consent is a process that is initiated prior to the individual's agreeing to participate in the study and continues throughout the individual's study participation. Consent forms will be

Institutional Review Board (IRB)-approved and the participant will be asked to read and review the document. The investigator will explain the research study to the participant and answer any questions that may arise. A verbal explanation will be provided in terms suited to the participant's comprehension of the purposes, procedures, and potential risks of the study and of their rights as research participants. Participants will have the opportunity to carefully review the written consent form and ask questions prior to signing. The participants should have the opportunity to discuss the study with their family or surrogates or think about it prior to agreeing to participate. The participant will sign the informed consent document prior to any procedures being done specifically for the study. Participants will have the option of consenting in REDCap. Participants must be informed that participation is voluntary and that they may withdraw from the study at any time, without prejudice. A copy of the informed consent document will be given to the participants for their records. The informed consent process will be conducted and documented in the source document (including the date), and the form signed, before the participant undergoes any study-specific procedures. The rights and welfare of the participants will be protected by emphasizing to them that the quality of their medical care will not be adversely affected if they decline to participate in this study.

10.1.2 Study Discontinuation and Closure

This study may be temporarily suspended or prematurely terminated by the Sponsor or the PI at any site if there is sufficient reasonable cause. Written notification, documenting the reason for study suspension or termination, will be provided by the suspending or terminating party to study participants, investigator, funding agency, the Investigational New Drug (IND) or Investigational Device Exemption (IDE) sponsor and regulatory authorities. If the study is prematurely terminated or suspended, the Principal Investigator (PI) will promptly inform study participants, the Institutional Review Board (IRB), and sponsor and will provide the reason(s) for the termination or suspension. Study participants will be contacted, as applicable, and be informed of changes to study visit schedule.

Circumstances that may warrant termination or suspension include, but are not limited to:

- Determination of unexpected, significant, or unacceptable risk to participants
- Demonstration of efficacy that would warrant stopping
- Insufficient compliance to protocol requirements
- Data that are not sufficiently complete and/or evaluable
- Determination that the primary endpoint has been met
- Determination of futility

Study may resume once concerns about safety, protocol compliance, and data quality are addressed, and satisfy the sponsor, IRB and/or Food and Drug Administration (FDA).

In terminating the study, the Sponsor and the Principal Investigator will assure that adequate consideration is given to the protection of the subjects' interests.

10.1.3 Confidentiality and Privacy

Participant confidentiality and privacy is strictly held in trust by the participating investigators, their staff, and the sponsor(s) and their interventions. This confidentiality is extended to cover testing of biological samples and genetic tests in addition to the clinical information relating to participants. Therefore, the study protocol, documentation, data, and all other information generated will be held in strict confidence. No information concerning the study or the data will be released to any unauthorized third party without prior written approval of the sponsor.

All research activities will be conducted in as private a setting as possible.

The study monitor, other authorized representatives of the sponsor, representatives of the Institutional Review Board (IRB), regulatory agencies or pharmaceutical company supplying study product may inspect all documents and records required to be maintained by the investigator, including but not limited to, medical records (office, clinic, or hospital) and pharmacy records for the participants in this study. The clinical study site will permit access to such records.

The study participant's contact information will be securely stored at each clinical site for internal use during the study. At the end of the study, all records will continue to be kept in a secure location for as long a period as dictated by the reviewing IRB, Institutional policies, or sponsor requirements.

Study participant research data, which is for purposes of statistical analysis and scientific reporting, will be transmitted to and stored at password-protected database. This will not include the participant's contact or identifying information. Rather, individual participants and their research data will be identified by a unique study identification number. The study data entry and study management systems used by clinical sites and by University of Pennsylvania School of Dental Medicine research staff will be secured and password protected. At the end of the study, all study databases will be de-identified and archived at password-protected database.

